3 STUDY IMPLEMENTATION

3.1 STUDY DESIGN

Fifteen patients with metastatic or primary hepatic malignancy will be enrolled to yield a minimum of ten evaluable patients. Prior to TACE, all patients will undergo conventional baseline imaging. The first five patients enrolled will receive a single dose of the study imaging agent (FMISO) post-TACE to determine imaging parameters and feasibility. Subsequent to the feasibility study, the remaining patients (#6-15) will receive the hypoxia imaging agent before and following TACE to determine changes in uptake pattern attributable to arterial embolization. Following TACE patients will be monitored according to standard of care until tumor progression is documented. Registration of functional and/or metabolic imaging demonstrating progression with immediate post-TACE hypoxia imaging will be performed for correlative analysis.

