3.3 IMAGE ANALYSIS

Feasibility of FMISO PET imaging post-TACE will be assessed by individually characterizing FMISO uptake in treated tumors as absent, background (equivalent to normal liver), or increased relative to liver background. Lesions demonstrating any increased activity compared to background liver will be further characterized as diffusely or focally increased activity.

Changes in FMISO PET activity before and following TACE will be descriptively compared and change in peak SUV will be assessed as response to embolization.

Individual liver tumors which demonstrate progression defined by increased size and/or enhancement will be evaluated for geographic FMISO uptake correlation. CT or MRI images demonstrating progression will be registered with FMISO PET-CT images automatically using OncoNav software (developed at the Center of Interventional Oncology) to determine whether qualitatively increased or decreased FMISO uptake is observed in spatial relation to tumor progression.

Increased FMISO activity which correlates positively with tumor progression will be further quantified using calculated standardized uptake values (SUV) or tumor-to- serum activity ratio in manually selected regions of interest (ROI).

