3.5.2 General Off-Study Criteria

- Inability to complete ¹⁸F-MISO imaging
 - Patients will be considered “unevaluable” for the study if [¹⁸F] FMISO imaging is incomplete or deficient and will be replaced (see Section 6.2.1). As an example, an FMISO scan which in the opinion of the Principal Investigator does not demonstrate hepatic uptake relative to background liver activity will be considered deficient and will not be included in the data analysis.
- Patient decides to withdraw from the study

- Toxicity which prevents further imaging (e.g. renal dysfunction defined as serum creatinine >2.0mg/dl which precludes CT or MRI imaging)
- Death
- Progression of disease
- Additional treatment of primary or metastatic hepatic malignancy (i.e., transplantation, resection)

The reason for study removal and the date the patient was removed must be recorded in the study database.

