3.7 STUDY STOPPING RULES

Enrollment will be halted; IRB will be notified if:

- Any grade 3 adverse event definitely attributed to [¹⁸F] FMISO (occurring within 24 hours of injection)
- Any grade 4 or grade 5 adverse event regardless of attribution
- Patients not receiving TACE at NIH CC will be observed for adverse events according to one or more of the following:
 - Patient must have physician willing to collaborate with NIH PI by providing required medical record and digital MR/ CT scan documentation pre and post TACE procedure
 - patients will be provided with the PI’s contact information to report symptoms which could represent an adverse event,
 - telephone call from the PI’s designee on the day following the FMISO scan to document signs or symptoms
- Patient(s) will be monitored until there is improvement or resolution of toxicity.
- Following review and approval by the IRB study enrollment will resume.

Enrollment will be limited to six patients if fewer than 2 patients demonstrate demonstrable ¹⁸F-FMISO uptake in liver tumors, consistent with diagnostic uptake of radiopharmaceutical in fewer than 30% of patients with liver cancer.

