6.2.3 Response Criteria

All of the patients who met the eligibility criteria (with the possible exception of those who could not undergo ¹⁸F-MISO imaging) should be included in the main analysis of the response to the imaging agent. All conclusions should be based on all eligible patients.

For the purposes of this study, patients with baseline CT or MRI and should be re-evaluated for response per standard of care approximately 4 to 6 weeks following TACE treatment with an abdominal CT and MRI. Scanning interval may be increased to 3 months instead of 4-6 weeks if stable disease is documented on at least two successive imaging studies obtained at the 4-6 week post-TACE interval.

Response and progression of only targeted tumors will be evaluated in this study using the revised modified Response Evaluation Criteria in Solid Tumors (mRECIST) guidelines.¹⁹

Complete Response (CR)	Disappearance of any intratumoral arterial enhancement
Partial Response (PR)	At least 30% decrease in the sum of the diameters of viable (enhancement in the arterial phase) target lesions, taking the baseline sum of the diameters of target lesions

Stable Disease (SD)	Any cases that do not qualify for either PR PD
Progressive Disease (PD)	An increase of at least 20% in the sum of the diameters of viable (enhancing) target lesion, taking as reference the smallest sum of the diameters of viable (enhancing) target lesions recorded since treatment started.

European Association for the Study of Liver, European Organization for Research and Treatment of Cancer. Journal of Hepatology, 2012 56:908-943.

Serum alpha-fetoprotein levels will be assessed and compared pre- and post-TACE per standard of care as a marker for tumor progression despite TACE. Cross-sectional and PET imaging will continue to be obtained at 4-6 week intervals until imaging evidence of disease progression is obtained and compared with FMISO imaging.

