8 STATISTICAL CONSIDERATIONS

The study is a proof of concept protocol. It aims to determine the feasibility of acute hypoxia imaging of the liver following TACE. Power and significance calculations are not applicable to this small sample feasibility study.

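### The 2-of-6 early stop is a cut-off on the observed rate that cannot exclude a true uptake rate of 30%, and the plan gives no proportion, interval or reference for feasibility if the trial continues.

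*Combined protocol and SAP*

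**What the plan says.** The uptake rule is in Section 3.7: "Enrollment will be limited to six patients if fewer than 2 patients demonstrate demonstrable" uptake of the tracer in liver tumours. The same sentence adds that this would be "consistent with diagnostic uptake of radiopharmaceutical in fewer than 30% of patients with liver cancer". No confidence level, error rate or stopping probability is attached, and the 30% figure for uptake appears nowhere else.

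Section 3.1 sets the size: "Fifteen patients with metastatic or primary hepatic malignancy will be enrolled to yield a minimum of ten evaluable patients". Section 3.3 assesses feasibility by "individually characterizing FMISO uptake in treated tumors as absent, background (equivalent to normal liver), or increased relative to liver background". This is a description of each tumour, with no patient-level count. Section 8 has no analysis of the primary objective and states: "Power and significance calculations are not applicable to this small sample feasibility study".

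Two further passages bear on who is counted. Section 3.5.2 gives, as an example of a deficient scan whose patient is replaced, one that in the investigator's opinion "does not demonstrate hepatic uptake relative to background liver activity will be considered deficient and will not be included in the data analysis". Section 6.2.3 says: "All conclusions should be based on all eligible patients", and allows a possible exception only for patients who could not undergo the imaging.

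**The concern.** The 30% clause is about patients with liver cancer in general, while the rule rests on six scans. If enrolment ends at six, the clause gives the report a ready-made sentence about the tracer, and nothing beside it tells the reader how often a tracer at or above 30% would stop in the same way.

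If enrolment continues, the gap is of another kind. The primary objective is to determine feasibility, yet after the sixth patient no stated quantity answers it. The sponsor thought 30% relevant enough to justify ending the trial early, but the final data are not set beside that figure, and no interval shows how precisely uptake was estimated. Feasibility would then be judged after the results are known.

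Both problems are worse if scans without uptake can leave the count, because those scans are the negatives that the rule and any final proportion depend on.

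**Working it through.** **Inputs.** Look at n = 6, stop if X ≤ 1, reference 30% (Section 3.7). Enrolment of 15 with at least 10 evaluable (Section 3.1). The documents give no confidence level, so the levels below (80% to 97.5% one-sided) are assumptions. I take demonstrable uptake in Section 3.7 to be the increased category of Section 3.3, and patients to be independent with a common rate p.

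**1. Reproducing the cut-off.** 0/6 = 0% and 1/6 = 16.7% lie below 30%; 2/6 = 33.3% lies above. Fewer than 2 of 6 is exactly the set of results with an observed rate below 30%, so the figure reproduces as a cut-off on the point estimate.

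**2. Stopping probability.** P(stop) = (1−p)^6 + 6p(1−p)^5. At p = 0.30 this is 0.1176 + 0.3025 = 0.420.

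| True rate | P(stop) |
|---|---|
| 20% | 0.655 |
| 30% | 0.420 |
| 40% | 0.233 |
| 50% | 0.109 |

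**3. What a triggering result excludes.** The exact (Clopper-Pearson) one-sided upper bound solves P(X ≤ x | n = 6, p) = 1 − level.

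| Result | 80% | 88% | 90% | 95% | 97.5% |
|---|---|---|---|---|---|
| 0/6 | 23.5% | 29.8% | 31.9% | 39.3% | 45.9% |
| 1/6 | 42.2% | 48.9% | 51.0% | 58.2% | 64.1% |

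Neither result excludes 30% at 90% or 95%. 0/6 does so up to about 88%; 1/6 does not even at 80%.

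**4. What a continuing trial can show.** It carries at least 2 positives forward. The lowest possible final result in 15 patients, 2/15 = 13.3%, has an upper bound of 36.3% (one-sided 95%) or 40.5% (the upper end of a two-sided 95% interval). Only 0/15 or 1/15 would bring the one-sided 95% bound below 30% (27.9% for 1/15), and those cannot occur once the look has been passed. At 95%, then, the final reading is either above 30% or inconclusive. For a reading above 30%:

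| Result | One-sided 95% lower bound | Two-sided 95% lower limit |
|---|---|---|
| 8/15 | 29.999% | 26.6% |
| 9/15 | 36.0% | 32.3% |
| 6/10 | 30.4% | 26.2% |
| 7/10 | 39.3% | 34.8% |

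On the one-sided bound, 9/15 or 6/10 is needed, with 8/15 just short. If the lower limit of a two-sided 95% interval is read instead, 9/15 still suffices, but with ten patients it takes 7/10.

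**5. The denominator.** Suppose one negative scan is ruled deficient and its patient replaced. The rule then stops only if at most 1 of 7 scanned patients is positive, with probability 0.329 at p = 0.30. With two such replacements (8 scanned) it is 0.255. Both compare with 0.420 when every completed scan counts. The proportion moves as well: 2 positives among 7 scanned is 28.6%, but 2/6 = 33.3% once one negative is dropped.

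**The case against.** The strongest reply is that the plan makes no inferential claim. Section 3.7 uses a phrase of consistency, not of proof, and every triggering result does have an observed rate below 30%. Section 8 disclaims significance calculations, so a 95% standard is the reader's import. A 42% chance of stopping at exactly 30% is ordinary for a cut-off placed there with six patients. The study is a proof-of-concept pilot, part of its objective is purely descriptive, and Section 3.3 does say how uptake will be characterised.

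Much of this stands. A reader might infer that the rule purports to show uptake below 30%, or that no triggering result could lend that any support. The documents do not bear out either reading: the wording is softer, no confidence level is set, and 0/6 excludes 30% at about 88% one-sided. Nor should one infer that a final 2/15 would itself demonstrate a rate below 30%. Its upper bound is 36%, so by the standard applied to 1/6 it is inconclusive too. It follows that setting the final interval beside 30% cannot by itself deliver a verdict of not feasible.

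The reply does not supply the rule's operating characteristics, or any patient-level estimate with its precision for the primary objective. Neither needs a power calculation. It also leaves open whether negative scans count. The example in Section 3.5.2 may be meant for technical failures only, but as written it can cover a completed scan that is simply negative.

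**Conclusion.** The point holds as a reporting and interpretation gap. The 2-of-6 rule is coherent as a pragmatic cut-off on the observed rate. It does not license a statement that true uptake is below 30%: a tracer at exactly 30% would be stopped 42% of the time and one at 40% would be stopped 23% of the time, and neither 0/6 nor 1/6 excludes 30% at 90% or 95% one-sided exact confidence. Past six patients, the primary feasibility question has no stated proportion, interval or reference.

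These figures assume independent patients, a common uptake rate and a fixed count of six in which every completed scan is included. The last assumption is not secure under Sections 3.5.2 and 6.2.3 as they stand; if negatives are replaced, the stopping probabilities fall and the proportion is inflated. Nothing here argues for a larger trial or a different boundary.

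**What to change.** - **Section 3.7.** Keep the boundary. Reword the 30% clause to say that the observed rate is below 30% and that this is a pragmatic early stop. State the stopping probabilities: 66%, 42%, 23% and 11% at true rates of 20%, 30%, 40% and 50%.
- **Section 8.** Report the proportion of patients with increased tumour uptake and its exact 95% confidence interval, at six patients if stopped and at the end otherwise, shown beside the 30% reference. Say in advance that a 15-patient trial that has continued can read only as above 30% or inconclusive, and whether above is judged on the one-sided bound (9/15 or 6/10) or on the two-sided interval (9/15 or 7/10).
- **Denominator.** Count patients whose completed scan shows no uptake, both in the six and in the final proportion. Reconcile the exclusion and replacement in Section 3.5.2 with the all-eligible-patients statement in Section 6.2.3, keeping technically failed scans distinct from negative ones.

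The cost is a few lines of text, with no added patients, scans or visits. The downside is that the early stop will carry a more modest stated meaning, and the reported interval will be wide.

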4 CONCOMITANT MEDICATION AND SUPPORTIVE CARE GUIDELINES

Patients will receive the standard of care supportive measures for patients undergoing DEB-TACE and additional care at the discretion of their primary oncology team.

5 BIOSPECIMEN COLLECTION

This protocol does not require bio-specimen collection. If specimens are obtained, they will be done so on another NCI protocol.

6 DATA COLLECTION AND EVALUATION

6.1 DATA COLLECTION

Data collection for this study will include imaging data used to identify acute post-embolization tumor hypoxia, as well as conventional post-treatment imaging and measurement of tumor markers used to identify tumor progression despite therapy. Other follow up data such as date of death will also be collected. The [¹⁸F] FMISO PET-CT imaging and post-treatment CT and MRI will be stored in PACS prior to image registration and analysis. PET-CT and conventional CT images will be transferred to a workstation for registration analysis. Identifiers will be removed from fused images for characterization of degree of overlap between documented tumor progression and acute post-treatment hypoxia. Imaging data including determination of response by mRECIST criteria as well as tumor marker levels will be collected in an Excel spreadsheet that will be stored in a password-protected PC kept in a secured office.

Grade 2 events and higher will be recorded in the study database. Grade 1 events will not be recorded or reported.

The PI will be responsible for overseeing entry of data into an in-house password protected electronic system and ensuring data accuracy, consistency and timeliness. The principal investigator, associate investigators/research nurses and/or a contracted data manager will assist with the data management efforts. Source data obtained during the conduct of the protocol will be kept in secure network drives or in approved alternative sites that comply with NIH security standards. Primary and final analyzed data will have identifiers so that research data can be attributed to an individual human subject participant.

End of study procedures: Data will be stored according to HHS and FDA regulations as applicable.

Loss or destruction of data: Should we become aware that a major breach in our plan to protect subject confidentiality and trial data has occurred, the IRB will be notified.

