6.2 RESPONSE CRITERIA

6.2.1 Definitions

6.2.1.1 Evaluable for toxicity

All patients will be evaluable for toxicity from the time of their first treatment with [¹⁸F] FMISO up to 24 hours post injection and any adverse events including allergic reactions, FMISO extravasation, or any Grade 3 or greater AE within the 24-hour time frame post injection will be followed until resolution.

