7 SAFETY REPORTING REQUIREMENTS/DATA&SAFETY MONITORING PLAN

7.1 DEFINITIONS

7.1.1 Adverse Event

An adverse event is defined as any reaction, side effect, or untoward event that occurs during the course of the clinical trial associated with the use of a drug in humans, whether or not the event is considered related to the treatment or clinically significant. For this study, AEs will include events reported by the patient, as well as clinically significant abnormal findings on physical examination or laboratory evaluation. A new illness, symptom, sign or clinically significant laboratory abnormality or worsening of a pre-existing condition or abnormality is considered an AE. All AEs must be recorded on the AE case report form unless otherwise noted above in Section **6.1**.

All AEs, including clinically significant abnormal findings on laboratory evaluations, regardless of severity, will be followed until return to baseline or stabilization of event. Patients will be evaluable for toxicity due to [¹⁸F] MISO for a period of one day after radiopharmaceutical administration (exceeding 10 half-lives of the radiopharmaceutical). An abnormal laboratory value will be considered an AE if the laboratory abnormality is characterized by any of the following:

- Results in discontinuation from the study
- Is associated with clinical signs or symptoms

- Requires treatment or any other therapeutic intervention
- Is associated with death or another serious adverse event, including hospitalization.
- Is judged by the Investigator to be of significant clinical impact
- If any abnormal laboratory result is considered clinically significant, the investigator will provide details about the action taken with respect to the test drug and about the patient's outcome.

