9.3 EVALUATION OF BENEFITS AND RISKS/DISCOMFORTS

9.3.1 Risk of IND agent

Although there has been no reported toxicity for the [¹⁸F] FMISO dose required for hypoxia imaging two potential risks common to radiopharmaceutical imaging agents that are possible include:

- Allergic reaction
- Extravasation of the imaging agent into the skin/subcutaneous tissue from Intravenous infiltration.

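### Section 6.1 keeps grade 1 events out of the study database, so it cannot document the follow-up of mild allergic reactions and FMISO extravasation that 6.2.1.1 and 7.1.1 require

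*Combined protocol and SAP*

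**What the plan says.** Section 6.1 sets the recording threshold: "Grade 2 events and higher will be recorded in the study database. Grade 1 events will not be recorded or reported".

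On follow-up, 6.2.1.1 covers "any adverse events including allergic reactions, FMISO extravasation, or any Grade 3 or greater AE within the 24-hour time frame post injection" and asks that these be followed until they resolve. The grade 3 threshold in that phrase is attached to other events; the two named events carry none. Section 7.1.1 is broader: all adverse events, "regardless of severity, will be followed until return to baseline or stabilization of event".

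On recording, 7.1.1 does not compete with 6.1. It says "All AEs must be recorded on the AE case report form unless otherwise noted above in Section" 6.1. Section 7.2.2 likewise exempts grade 1 events from the continuing-review report.

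Section 9.3.1 names two potential risks of the agent: allergic reaction and "Extravasation of the imaging agent into the skin/subcutaneous tissue from Intravenous infiltration". Radiation is treated separately in 9.3.1.1.

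Under 3.1, the first five patients are injected once, after TACE, and patients 6 to 15 are injected before and after TACE. Section 3.3 compares the paired scans descriptively and states that "change in peak SUV will be assessed as response to embolization".

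**The concern.** The protocol singles out two events for follow-up whatever their grade, and they are the same two it names as risks of the agent. It then keeps the mildest grade of both out of the database. A monitor or analyst working from the database could not see that a grade 1 reaction or infiltration began, was followed, or ended. The final report could not give a complete frequency for either risk. Sections 1.2.2 and 10.2.2 rest the agent's safety on an absence of reported toxicity, so a complete count of these two events is among the few safety results this small study can add. Ten of the fifteen patients are exposed twice.

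Extravasation also raises a measurement question that has nothing to do with its grade. SUV is tissue activity normalized to the activity assumed to have been injected. If part of the dose stays at the injection site, SUV is too low, and a before-to-after change in peak SUV is distorted. The protocol specifies no injection-quality variable that would let an analyst identify such a scan.

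**Working it through.** **Part 1: the passages side by side**

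| Question | 6.1 | 6.2.1.1 | 7.1.1 | 7.2.2 |
|---|---|---|---|---|
| Record grade 1? | No | Silent | Yes, except as 6.1 provides | Not addressed |
| Report grade 1? | No | Silent | Not addressed | Not required |
| Follow a grade 1 allergic reaction or extravasation? | Silent | Yes, to resolution | Yes, any severity | Not addressed |

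On recording and reporting, the sections agree. The tension is between the duty to follow (6.2.1.1, 7.1.1) and the absence of a database entry in which that follow-up would appear (6.1).

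*Exposure.* Inputs from 3.1: 5 patients with one injection, 10 patients with two. Planned injections = 5 × 1 + 10 × 2 = 25, of which 20 form 10 pairs. The optional 240-minute scan in 3.2 uses the same injection and adds none.

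*What a zero would mean.* With complete recording and no events in 25 injections, treated as independent, the one-sided 95% upper limit on the rate is 1 − 0.05^(1/25) = 11.3%. Under 6.1, a zero in the database gives that limit only for grade 2 or higher events and says nothing about grade 1.

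**Part 2: SUV, illustration only**

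The documents give neither an extravasation rate nor a fraction of dose lost, so both are assumed here.

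Let f be the fraction of the recorded dose that does not reach the circulation. Measured SUV = (1 − f) × true SUV. With no true change:

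- post-TACE injection affected: apparent change = −f
- pre-TACE injection affected: apparent change = 1/(1 − f) − 1

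| f | Post-TACE affected | Pre-TACE affected |
|---|---|---|
| 10% | −10% | +11% |
| 20% | −20% | +25% |
| 30% | −30% | +43% |

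If the summary were a mean over 10 pairs (3.3 does not say), one affected pair would move it by a tenth of the table entry: 1 to 3 percentage points down, or 1.1 to 4.3 up.

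For a per-injection rate p, the chance of at least one event in 25 injections is 1 − (1 − p)^25. The expected number of affected pairs is 10 × [1 − (1 − p)²].

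| p (assumed) | At least one in 25 | Expected affected pairs of 10 |
|---|---|---|
| 1% | 22% | 0.2 |
| 5% | 72% | 1.0 |
| 10% | 93% | 1.9 |
| 15% | 98% | 2.8 |

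*What is not affected.* The visual reading in 3.3 compares tumor with liver, and the alternative measure is a tumor-to-serum ratio. Numerator and denominator both scale with delivered activity, so to first order (1 − f) cancels in each.

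**The case against.** The strongest reply is that there is no contradiction. Following a patient and entering an event in a database are different acts, and the protocol chose not to enter grade 1 events: 7.1.1 points to 6.1, and 7.2.2 is consistent with both. This stands. A reader might infer that 6.1 and 7.1.1 conflict on recording; they do not.

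A reader might also infer that mild events leave no trace at all. The documents do not support that. Section 6.1 provides for source data to be kept, 7.5.1 has the team discuss any adverse event and the principal investigator review each patient's data, and 3.7 lists a next-day call documenting symptoms as one option for patients not treated with TACE at NIH. For the same reason, it does not follow that the team would be unaware of a mild first reaction when the second injection is given. What remains is that none of these channels yields a complete count in the study dataset.

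A third tempting inference is that the grade 1 rule lets under-dosed scans into the SUV comparison unnoticed. It does not follow. Adverse-event grade measures clinical severity, not activity lost. A recorded grade 2 extravasation would not flag a scan under this plan either, and a symptomless infiltration may not be an adverse event at all. In addition, 3.5.2 lets the principal investigator exclude a deficient scan, with hepatic uptake given only as an example, and 10.6 defers to PET department guidelines that are not in the documents and may include a site check. These points make the SUV matter separate and smaller. They do not supply a written criterion or a data field.

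Finally, CTCAE 4.0 is cited in 6.3 but not reproduced, so which mild events fall in grade 1 cannot be checked here.

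**Conclusion.** The point holds in a limited form. As written, the study database can neither show that grade 1 allergic reactions and extravasations were followed to resolution nor give a complete count of the two risks in 9.3.1, over as many as 25 injections. This rests on the text alone, with one assumption: that some of these events would be graded 1. It is a gap between follow-up and documentation, not a dispute over the recording rule and not evidence that events go unnoticed.

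The SUV matter is secondary and independent of grading. The arithmetic is sound, but its size depends entirely on assumed loss fractions and rates. It touches SUV values, chiefly a descriptive comparison in at most 10 pairs in a study that section 8 says has no power or significance calculations. The visual feasibility reading is largely protected.

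**What to change.** In 6.1, add one exception: any allergic reaction or extravasation within 24 hours of an FMISO injection is entered in the study database at any grade, with its resolution. Other grade 1 events stay exempt, which keeps 6.1 in line with 7.2.2.

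Separately, add a field to the PET dosing record noting for each injection whether infiltration was observed, with or without symptoms. In 3.3, state that a scan with observed infiltration is flagged, stays in the visual classification, and stays in the main SUV-change summary, and that this summary is repeated without flagged pairs as a sensitivity analysis. Flagging is preferable to mandatory exclusion, because with at most 10 pairs each exclusion costs at least a tenth of the data and a minor infiltration may matter little. The flag also gives the discretion in 3.5.2 recorded information to act on.

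The cost is one sentence in 6.1, a line in 3.3, and slight extra data entry for about 25 injections. No dose, schedule or clinical rule changes.
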